Measures will be obtained at clinic visits at Baseline and ~quarterly for 1 year. Primary outcomes are change in HbA_{1c} and the Diabetes Self Management Profile Self-Report Form total score over 1 year. Other planned measures will be reviewed and refined by the Adolescent and Parent Crowds during RCT planning. To promote retention, encourage timely completion of questionnaires and minimize missing data, each adolescent will receive \$40 credited to a gift card when all measures scheduled for a given study visit are completed. Also, adolescents will receive a \$10 bonus if they complete all of the questionnaires within 7 days of the research team's e-mail containing a link to the REDCap platform for questionnaire administration at Baseline, 6 and 12 months. Online completion of questionnaires will be available for those with internet access using REDCap. Those who do not complete questionnaires online before visits can do so at visits via PC, tablet or hard copy or online during TC visits. Table 3 shows the measurement schedule, including estimated participation burden per measure. Respondents are indicated by A (Adolescent), P (Parent) or HCP (Health Care Provider). Participation burden has been minimized in several ways. Questionnaire completion is limited to study visits at 0, 6 and 12 months rather than every quarterly visit. Questionnaire completion time at the Baseline visit is 75-80 minutes for parents and adolescents and 65-70 minutes at 6 and 12 months. Online completion of questionnaires via REDCap can minimize inconvenience by enabling participants to complete questionnaires at convenient times or over several distinct periods.

Table 3. Measurement schedule.

Measures	Burden (Min/Visit)	~Quarterly Clinic Visits				
		0	3	6	9	12
Demographic Information (P)	10	•				
HbA _{1c} ; Device downloads; Glycemic variability; Hypoglycemia Diary (A,P)	20	•	•	•	•	•
Appointment keeping; Health Care Use, Costs, Time expended (P; EMR)	5	•	•	•	•	•
Type 1 Diabetes and Life Measures (A,P)	15	•		•		•
Diabetes Self Management Profile-Self Report (A,P)	15	•		•		•
Problem Areas in Diabetes Scale (A,P)	15	•		•		•
Collaborative Parent Involvement Scale (A)	5	•		•		•
Family-Centered Care Self-Assessment Tool (A,P)	10	•		•		•
Diabetes-Specific Risk-Taking Inventory (A)	10	•		•		•
Readiness Assessment for Emerging Adults with Diabetes Diagnosed in Youth (A)	5	•		•		•
Diabetes Care Inventory (HCP)	5					•

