Analytic Plans Primary endpoints are change in HbA_{1c} and DSMP-SR total score (treatment adherence) over 1 year. Secondary endpoints are: # of severe hypoglycemic events (Hypoglycemia Diary); measures of glycemic variability at each visit; and questionnaires obtained quarterly. The Full Analysis Set will include those who provide data at ≥ 1 follow-up visit. The Completer Analysis set will include those who provide data at all follow-ups. Efficacy analyses will be done on both sets.³¹³⁻³¹⁵ We will use multiple imputation for treatment of missing data.³¹³⁻³¹⁵ Obtained data will be summarized in graphs and tables. Categorical variables will be summarized by frequencies and percentages; continuous variables by mean, median, standard deviation (or SEM), minimum and maximum. Data will be summarized by primary group (UC and TC), secondary group (TC-TH, TC-IP, TC-IP/TH, TC-TH/CH) and measurement points.^{316,317} Model assumptions will be checked before analyses, and appropriate transformations or non-parametric methods will be used when indicated. For summarization of normally distributed data, group means and SEM will be presented. In case of substantial deviation from normality, boxplots will be presented. Exploratory subgroup analyses (e.g. race, ethnicity, gender, SES, secondary group) will be conducted as needed.^{318,319} Most tests will be performed against a two-sided alternative at the $\alpha = 0.05$ significance level and a 95% confidence interval and/or a p-value will be provided for inferential purposes. Data from both clinics will be pooled for analyses.^{316,317} All analyses will be done using the most recent version of SAS, SPSS, R or M-Plus.³¹⁵⁻³²² Demographic variables (age, gender, race, ethnicity, family structure, marital status, SES) and baseline values of primary and secondary end points, and questionnaire results will be summarized by group. If the normality assumption holds, t-tests of continuous baseline variables and Fisher exact test/chi-square test/CMH test for categorical variables will be used to compare the TC and UC groups at baseline; one-way ANOVA will be used for comparisons of secondary groups. The statistician will select analytic methods based on data distributions and any imbalanced baseline scores.³²³ Linear mixed effects modeling (continuous outcomes) or generalized linear mixed modeling (categorical outcomes) is planned for the hypotheses below.³¹⁵⁻³²² Treatment group (UC vs TC) and demographic characteristics will be fixed effects in these models, while site, physician, and within-subject effects will be random effects. The same analyses will be attempted for secondary groups, sample size permitting. We will use Holmbeck's methods³²⁴ to evaluate baseline demographic variables and questionnaire scores as moderators of TC-UC effects on primary outcomes and to evaluate mediation of effects on primary endpoints. Candidate mediators are variables that are obtained serially concurrent with the primary endpoints at ≥ 3 visits.

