
Sample Size and Statistical Power: Recruitment ended at the end of March 2020. A total of 115 families were recruited. Allowing for some attrition prior to randomization, a sample of 100 patients (65 TC and 35 UC) yields 87.4% power to detect a clinically meaningful group differences in mean HbA_{1c} of 0.5% (~0.7 SD) versus the alternative of equal means using a t test with $p = .05$. Limiting recruitment to those with HbA_{1c} = 7.5-10.0% is anticipated to reduce the SD from 1.5% for the general adolescent T1D population to 0.7%, boosting effective statistical power for the RCT. The predicted 12-month means are 8.1% (TC) and 8.6% (UC). If the SD is 1.0%, our power is reduced to 71.3%; if it is 1.5% as in the general population, our power is 50.9%. This sample size also achieves power of 78.2% to detect a clinically meaningful mean differences in the DSMP-SR

total score of 7.0 points (~0.6 SD) at 1 year. The estimated mean values are 63.0 (TC) and 56.0 (UC). This preliminary trial will yield rich data that could be used to guide the sampling plan for a future, more ambitious, multi-center trial.³²⁵⁻³²⁷ The following hypotheses will be tested:

Hypothesis 1: Compared with UC patients, those randomized to TC will have significantly more favorable primary (HbA_{1c} and DSMP-SR scores) and secondary (frequency of severe hypoglycemia and level of glycemic variability) diabetes management outcomes at their 6, 9, and 12 month follow-up visits.

Hypothesis 2: Compared with UC patients, those randomized to TC will demonstrate more favorable scores on the T1DAL, PAID, and CPI at follow-up measurements.

Hypothesis 3: Significantly higher scores will be obtained on the DCI completed by HCPs describing TC care compared to HCPs describing UC care.

Hypothesis 4: Effects of TC on HbA_{1c} and DSMP-SR scores will be moderated by demographic variables (youth age, family SES, # of adult caregivers in the home) and by baseline scores on the T1DAL, PAID, and CPI. More benefit from TC will accrue to youth who are younger, from two-parent families with higher SES, and with more favorable scores on the T1DAL, PAID and CPI.

Hypothesis 5: Effects of TC on HbA_{1c} and DSMP-SR scores will be mediated by changes in scores on the T1DAL, PAID, and CPI. More benefit from TC will accrue to youth with favorable changes in T1DAL, PAID and CPI scores during the 12 months of the study.

[figure not shown]

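### The listed mixed-model terms leave the primary contrast unclear: the response is not stated, and visit, treatment-by-visit, baseline outcome and the randomisation strata are not listed

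*Combined protocol and SAP*

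**What the plan says.** All places are in section 3.4 of the combined protocol and SAP.

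- **Endpoint.** Analytic Plans names change in HbA1c and in "DSMP-SR total score (treatment adherence) over 1 year" as primary. It does not say whether the model's response is a single 12-month change, change at each visit, or raw values with or without the baseline row.
- **Model terms.** A linear mixed model is planned for continuous outcomes: "Treatment group (UC vs TC) and demographic characteristics will be fixed effects in these models". The random part of the model is listed as site, physician and within-subject terms. The same paragraph spells out what counts as demographic (age, gender, race, ethnicity, family structure, marital status, SES) and names baseline endpoint values separately, so the word does not cover baseline HbA1c or insulin modality.
- **Strata.** Experimental Design stratifies randomisation by insulin modality and by HbA1c at 8.7%.
- **Baseline.** "The statistician will select analytic methods based on data distributions and any imbalanced baseline scores".
- **Power.** The calculation rests on month-12 values ("The predicted 12-month means are 8.1% (TC) and 8.6% (UC") and on a 7.0-point DSMP-SR difference at 1 year.
- **Hypothesis 1.** It claims better "diabetes management outcomes at their 6, 9, and 12 month follow-up visits", and DSMP-SR is among those outcomes.
- **Schedule.** Analytic Plans lists as secondary endpoints "measures of glycemic variability at each visit; and questionnaires obtained quarterly". The Measurement Schedule says otherwise: "Questionnaire completion is limited to study visits at 0, 6 and 12 months rather than every quarterly visit".

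**The concern.** A treatment main effect with no visit or treatment-by-visit term gives one number for the whole follow-up. Hypothesis 1 needs a number for each visit, and the power calculation concerns month 12. Two analysts following the paragraph could report different quantities as the primary result, and their sizes would depend on how quickly the effect appears, which the documents do not state.

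Two further matters concern precision and prespecification. Baseline outcome and strata are collected, but the plan does not commit to using them. The method may also be chosen after baseline imbalance has been seen. A smaller drafting conflict is that a 9-month DSMP-SR effect is claimed for a visit at which the questionnaire is not given.

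**Working it through.** **Inputs from the documents:** 65 TC and 35 UC; two-sided 0.05; HbA1c difference 0.5; SD 0.7, with 1.0 as the plan's own alternative; DSMP-SR difference 7.0; HbA1c at 0, 3, 6, 9 and 12 months; DSMP-SR at 0, 6 and 12.

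**Assumptions, because the documents give no values:** a common correlation ρ between any two visits (0.3 or 0.6), the shape of onset, and equal SD at all visits unless stated.

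**The plan's own power figures.** A noncentral t with 98 df and noncentrality δ / (SD × √(1/65 + 1/35)) = δ / (0.2097 × SD) gives:

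| Case | Stated | Recomputed |
|---|---|---|
| HbA1c, SD 0.7 | 87.4% | 92.1% |
| HbA1c, SD 1.0 | 71.3% | 65.6% |
| HbA1c, SD 1.5 | 50.9% | 35.0% |
| DSMP-SR, 0.6 SD | 78.2% | 80.9% |

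The stated figures do not reproduce. That is a separate matter and nothing below depends on it; comparisons use the recomputed values.

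**What the listed coefficient estimates.** With balanced visits and a random intercept, the treatment main effect is the simple mean of the visit-specific differences. Take a true month-12 HbA1c difference of 0.50. Linear onset means 0.125, 0.25, 0.375 and 0.50 at months 3, 6, 9 and 12.

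| Rows used as response | Linear onset | Constant effect |
|---|---|---|
| Months 0 to 12 | 1.25/5 = 0.25 | 2.0/5 = 0.40 |
| Months 3 to 12 | 1.25/4 = 0.31 | 2.0/4 = 0.50 |
| Months 6 to 12 (Hypothesis 1 visits) | 1.125/3 = 0.375 | 1.5/3 = 0.50 |

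For DSMP-SR with a true 7.0 at month 12 and linear onset, averaging months 6 and 12 gives (3.5 + 7.0)/2 = 5.25; including the baseline row gives 10.5/3 = 3.5.

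**Power of the average.** The SD of the mean of four follow-ups is SD × √((1 + 3ρ)/4). At SD 0.7, with ρ = 0.3 then 0.6, linear onset gives 86.4% then 71.2% and a constant effect gives 99.8% then 98.1%. Month 12 alone, on raw values, gives 92.1%. Averaging can therefore lose or gain power.

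**Value of baseline at month 12.** The SD multipliers are 1 for raw values, √(2(1 − ρ)) for change and √(1 − ρ²) for baseline-adjusted values. At SD 1.0:

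| ρ | Raw | Change | Adjusted |
|---|---|---|---|
| 0.3 | 65.6% | 51.4% | 69.7% |
| 0.6 | 65.6% | 75.2% | 83.9% |

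The gain of adjustment over raw is 4.1 then 18.3 points; over change it is 18.3 then 8.7.

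**Unequal SDs.** Eligibility limits HbA1c to 7.5-10.0% at entry but not at follow-up, so the baseline SD may be smaller. With 0.7 at baseline and 1.0 at month 12, the SD of change is √(0.49 + 1 − 1.4ρ), which is 1.034 then 0.806. Change then gives 62.7% then 83.4%. The gain over change falls to 7.0 then 0.5 points; the gain over raw is unaffected.

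**The case against.** The strongest reply is that the sentence on model terms is a general outline for all six hypotheses, including Hypothesis 3 on the Diabetes Care Inventory, which is collected once. It is not a formula for the primary model. That is fair: the charge is under-specification, not a model known to miss its target. If the response is one 12-month change per patient, the treatment coefficient targets the right quantity, although the within-subject random effect then has no repeated data to act on.

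The plan also has baseline adjustment in view. The reference cited at the sentence on imbalanced scores is, by its title, about adjusting for baseline measures. But the adjustment remains conditional on what is observed, so that part of the concern stands.

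Four stronger readings are tempting, and the documents do not support them:

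- *That month 12 is the only timepoint named.* It is the powered one. The endpoint is change over 1 year, and Hypothesis 1 lists 6, 9 and 12 months without ranking them.
- *That the averaged coefficient equals the month-12 effect only if the effect is constant or the response is a single value.* Any pattern averaging to the month-12 value will do, for example 0.5, 0.6, 0.4, 0.5.
- *That omitting baseline or strata biases the comparison.* It costs precision; randomisation still protects the contrast.
- *That averaging must lose power.* The figures above go both ways.

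**Conclusion.** The concern holds as a gap in specification that should be fixed. On the natural repeated-measures reading, the listed treatment coefficient is a visit average. In general it is not the powered 12-month difference, and the listed terms cannot give the visit-specific effects in Hypothesis 1. Under an assumed linear onset to 0.50, the mismatch ranges from 0.125 (0.375 against 0.50) to 0.25 (0.25 against 0.50). With a constant effect and follow-up rows only, there is none.

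The firm part is that the target is unclear. The power figures depend on assumed correlations, onset and SDs. The advantage of baseline adjustment over raw month-12 values needs only a nonzero baseline correlation large enough to repay the degree of freedom it uses. Its advantage over change is sensitive to the SDs and can be as small as 0.5 points in the cases examined.

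**What to change.** In Analytic Plans:

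1. Use follow-up values as responses: HbA1c at 3, 6, 9 and 12 months; DSMP-SR at 6 and 12.
2. Prespecify as fixed effects treatment, categorical visit, treatment-by-visit, the continuous baseline value of the outcome, insulin modality, baseline HbA1c or its 8.7% stratum, and demographic covariates by name. Model within-person correlation.
3. Name the month-12 TC minus UC contrast as primary, to match the powering. With baseline as a covariate this contrast is the same for value or change, so the endpoint is kept.
4. Report the 6- and 9-month HbA1c and 6-month DSMP-SR contrasts from the same models, and state their status.
5. Remove observed baseline imbalance as a basis for choosing the primary method.
6. Correct the 9-month DSMP-SR claim in Hypothesis 1 and the statement on quarterly questionnaires, so that both match the 0-, 6- and 12-month schedule.

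The cost is SAP wording and a few degrees of freedom; every variable is already collected. Going from 98 to 88 error df lowers adjusted month-12 power by about 0.1 point (69.7% to 69.6% at SD 1.0, ρ = 0.3).

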Participants: The RCT would test the TC model with appropriate clinical candidates who could benefit from a relatively low intensity intervention but who may not need more intensive psychological services. We will enroll 150 Nemours T1D patients at Nemours Children’s Hospital (NCH) in Orlando, FL, or the Alfred I. du Pont Hospital for Children (AIDHC) in Wilmington, DE (~75/site), including ~21 African American and ~21 Hispanic youth (~28% minorities). The Facilities and Resources section confirms the feasibility of the sampling plan. Each parent/youth will sign IRB-approved Parental Permission and Assent Forms prior to participation. State laws require that participants in telehealth sessions must all be physically present in a state in which the participating HCPs are licensed and the team will ensure this. Youth eligibility criteria are: Age, ≥ 11 and < 17 yrs old; T1D for > 1 yr; Most recent HbA_{1c} or mean HbA_{1c} over the prior year 7.5-10.0%, inclusive; Able to complete questionnaires in English; No other medical obstacles to participation per the treating MD; No concurrent enrollment in other T1D studies, and no T1D clinic visits in the preceding 12 months in which two or more care providers saw the patient together. Parent eligibility criteria are: Biological parent/legal caregiver of an enrolled patient; At least weekly involvement in T1D care; Able to complete questionnaires in English; Plans to continue T1D care at Nemours for > 1 yr; No reporting of the family for child protection complaints within the prior 3 years. Two parents of the same child may enroll, but they would jointly complete one set of questionnaires. HCPs (MDs, Advanced Practice Nurses, Dietitians, Social Workers and Psychologists) who have provided care to study participants also contribute data and will provide informed consent.

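### The HbA1c power takes its SD of 0.7% from the entry window, but that is the spread of the entry value; nothing supports it for 12-month HbA1c or for change

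*Combined protocol and SAP*

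**What the plan says.** In section 3.4, under Sample Size and Statistical Power, the plan states that "a sample of 100 patients (65 TC and 35 UC) yields 87.4% power" to detect a 0.5% difference in mean HbA1c, which it equates to about 0.7 SD, by a t test at .05. The SD is justified by eligibility: "Limiting recruitment to those with HbA_{1c} = 7.5-10.0" percent "is anticipated to reduce the SD from 1.5% for the general adolescent T1D population to 0.7" percent. The outcome in that calculation is the value at one year: "The predicted 12-month means are 8.1% (TC) and 8.6% (UC"). The same paragraph gives lower power if the SD is 1.0% (71.3%) or 1.5% (50.9%).

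The window itself is defined under Participants in Part 2 of the same section. It applies to the most recent HbA1c or to the "mean HbA_{1c} over the prior year 7.5-10.0%, inclusive". Both are pre-enrolment quantities.

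Analytic Plans names change in HbA1c over one year as a primary endpoint, to be analysed by a linear mixed model. It also says "Most tests will be performed against a two-sided alternative".

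**The concern.** An eligibility window narrows the variable it selects on. It narrows a later measurement only to the extent that the two are correlated, and follow-up values are free to leave the window. The plan moves from a restricted entry value to a restricted outcome with no intermediate step, and the resulting SD is less than half the population figure it starts from.

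HbA1c is one of two primary endpoints. If 0.7% is too small for the analysed quantity, the headline power is too high and a null result would seem to rule out more than it does. The power paragraph also says that this trial may guide the sampling plan of a larger multi-center trial, so an entry-value SD taken for an outcome SD could be carried forward.

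**Working it through.** **Inputs from the plan.** 65 TC and 35 UC; difference 0.5%; t test at .05, taken as two-sided; population SD 1.5%; trial SD 0.7%; window 7.5-10.0%.

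**Inputs assumed.** The population correlation r between entry and 12-month HbA1c is not given, so 0.5 to 0.9 is shown. The relation is taken as linear with constant residual variance, and the population SD as 1.5% at both times. The population mean is set at 8.7%.

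**1. The plan's own figures.** The standard error of the difference is SD × sqrt(1/65 + 1/35) = SD × 0.2097. At SD 0.7 this is 0.147, the noncentrality is 0.5/0.147 = 3.41, and power on 98 degrees of freedom is 92.1%, against the printed 87.4%. At SD 1.0 it is 65.6% (printed 71.3%), and at SD 1.5 it is 35.0% (printed 50.9%). One-sided tests, other alphas and other splits were tried; none reproduced all three printed figures. That arithmetic is a separate matter. Below, each SD is compared with the 92% that SD 0.7 gives under the same test.

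**2. Where 0.7% comes from.** A normal with SD 1.5 truncated to 7.5-10.0 has SD 0.68-0.69 for any population mean from 8.0 to 9.5. A uniform distribution on the window has SD 2.5/sqrt(12) = 0.72. The plan's 0.7% is therefore almost exactly the SD of the selected entry value.

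**3. What that implies for the outcome.** Let V = 0.689² = 0.474 be the entry variance after selection, and 1.5² = 2.25 the population variance.

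- 12-month value: SD = sqrt(r²V + (1 − r²) × 2.25)
- Change: SD = sqrt((1 − r)²V + (1 − r²) × 2.25)
- Baseline-adjusted residual: SD = 1.5 × sqrt(1 − r²)

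Example at r = 0.7: the 12-month SD is sqrt(0.49 × 0.474 + 0.51 × 2.25) = sqrt(1.380) = 1.17.

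| r | 12-month SD | power | change SD | power | adjusted SD | power |
|---|---|---|---|---|---|---|
| 0.5 | 1.34 | 42% | 1.34 | 42% | 1.30 | 44% |
| 0.6 | 1.27 | 46% | 1.23 | 48% | 1.20 | 50% |
| 0.7 | 1.17 | 52% | 1.09 | 58% | 1.07 | 60% |
| 0.8 | 1.06 | 61% | 0.91 | 74% | 0.90 | 75% |
| 0.9 | 0.90 | 75% | 0.66 | 95% | 0.65 | 95% |

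**4. What would be needed to reach 0.7%.** For the 12-month value, an SD of about 0.71 needs r of about 0.99. For the residual, r = sqrt(1 − (0.7/1.5)²) = 0.884; for change, r is about 0.886.

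**5. Whether the window supplies it.** The residual SD contains no term for the window. For change, the SD without any window would be 1.5 × sqrt(2(1 − r)): 1.50, 1.34, 1.16, 0.95 and 0.67 for r from 0.5 to 0.9, against 1.34, 1.23, 1.09, 0.91 and 0.66 with it. So an SD near 0.7 for either quantity would come from a high correlation. The window contributes little or nothing.

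**The case against.** Three points deserve weight.

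First, the plan discloses what happens at SD 1.0% and 1.5%, and these nearly bracket the 12-month SDs above. A reader is told that power could be about half. This stands, and it limits the fault to the choice of expected case. The disclosure is weaker than it looks, because a two-sided test gives 65.6% and 35.0% at those SDs.

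Second, the endpoint is change, with quarterly HbA1c and a mixed model, so the raw 12-month SD may be the wrong yardstick. This also stands in part: at r near 0.9, change or baseline adjustment gives about 95% power. But the power text describes a plain t test on 12-month means, Analytic Plans does not name baseline HbA1c as a covariate, and the stated reason for 0.7% would still be wrong even if the number proved right.

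Third, the SDs in the table come from an assumed model. HbA1c may be skewed, and mid-range patients may vary less than a population whose 1.5% includes its extremes; a slope of 0.7 with a residual SD of about 0.5 would give about 0.7% at 12 months. A reader might therefore infer that the window cannot produce 0.7%. The documents do not support that; they support only that no evidence is offered for it.

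A reader might also make much of the either/or entry rule (latest value or yearly mean). It means that the latest value need not lie in the window, but in simulation it moved the 12-month SD only from 1.17 to 1.18 (r = 0.7) and from 0.90 to 0.92 (r = 0.9). The point does not depend on it.

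**Conclusion.** The point holds as a missing justification. The plan credits the entry window with an outcome SD of 0.7%; the window restricts only pre-enrolment HbA1c, and 0.7% matches the SD of that restricted value. No correlation, SD of change or follow-up SD links it to the outcome, so the headline power rests on an unsupported SD.

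The size depends on a correlation that the documents do not give. Over 0.5 to 0.9, power runs from values in the low forties up to 75% for the 12-month value and 95% for change or a baseline-adjusted analysis. It would be tempting to conclude that the trial had roughly an even chance of detecting 0.5%. That describes only correlations of about 0.5 to 0.7 and is not established. Confidence is high that 0.7% is unsupported for the outcome, and much lower about which SD should replace it.

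**What to change.** In Sample Size and Statistical Power:

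1. Remove the statement that the entry window reduces the outcome SD to 0.7%, and label 0.7% as the approximate SD of the entry value.
2. Say which quantity the power SD describes (12-month value, change, or residual after baseline adjustment) and give the correlation or data behind it. The COVID-19 section says that about one third of TC-IP families had completed by March 2020, so some follow-up HbA1c should exist. The SD pooled across arms, without unblinding, would serve. If the true difference were 0.5%, pooling would add 0.65 × 0.35 × 0.25 = 0.057 to the variance, taking an SD of 0.70 only to 0.74.
3. Restate the HbA1c power over a range of that SD, recomputing every figure for the 65/35 split. A replacement such as 1.0-1.3% should not be adopted without a source, since it would also be an assumption.

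The cost is one pooled SD calculation and a rewritten paragraph. Recruitment has closed, so enrolment is unaffected. The downside is a stated power that is likely to be less favourable.

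### The three HbA1c power figures (87.4%, 71.3%, 50.9%) do not follow from 65 versus 35 with a t test at .05; two-sided they are 92.1%, 65.6% and 35.0%

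*Combined protocol and SAP*

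**What the plan says.** All the inputs are in section 3.4 of the combined protocol and SAP. The paragraph on sample size and statistical power says that "a sample of 100 patients (65 TC and 35 UC) yields 87.4% power" for a 0.5-point difference in mean HbA1c (predicted 12-month means 8.1% for TC and 8.6% for UC), "versus the alternative of equal means using a t test with $p = .05". The base-case SD is 0.7, which the plan expects to result from limiting entry to HbA1c 7.5–10.0%. It gives two sensitivity cases: "If the SD is 1.0%, our power is reduced to 71.3%; if it is 1.5% as in the general population, our power is 50.9" per cent.

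The power paragraph does not state sidedness. The analytic plans, just before it, do: "Most tests will be performed against a two-sided alternative at the $\alpha = 0.05$ significance level". The section on COVID-19 changes confirms that the primary comparison pools all TC arms against UC. The plan gives no baseline correlation, covariate gain or dropout rate after randomization as a power input; it mentions only attrition before randomization.

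**The concern.** With the difference, arm sizes and test fixed, power depends only on the SD, so each figure can be checked directly. Moving from an SD of 0.7 to 1.5 more than halves the standardized difference, yet the stated power falls only from 87.4% to 50.9%. That is too shallow a fall for any one design.

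HbA1c is a primary endpoint, and these sentences are the plan's only statement of how well the reduced trial (150 planned, 115 recruited, 100 used for power) withstands a larger SD. The SD of 0.7 is an expectation, so the sensitivity cases matter. A reader would conclude that the trial keeps better-than-even power even at the general-population SD. That reading could lend too much weight to a null result, and it could carry an optimistic SD–power relation into planning for the later multi-center trial.

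**Working it through.** **Inputs (all from section 3.4).** n₁ = 65, n₂ = 35; difference 0.5; SD 0.7, 1.0 or 1.5; t test, alpha .05, two-sided as in the analytic plans.

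**Formula.** Noncentrality λ = (0.5/SD) × √(n₁n₂/(n₁+n₂)) = (0.5/SD) × √(65 × 35/100) = (0.5/SD) × 4.770. Power is the probability that a noncentral t with 98 df and noncentrality λ falls outside ±1.984.

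**Attempt to reproduce the plan's figures**

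| SD | λ | Two-sided power | Stated | Stated minus computed |
|---|---|---|---|---|
| 0.7 | 3.407 | 92.1% | 87.4% | −4.7 |
| 1.0 | 2.385 | 65.6% | 71.3% | +5.7 |
| 1.5 | 1.590 | 35.0% | 50.9% | +15.9 |

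A simulation of 40,000 trials per SD gives 92.0%, 65.7% and 34.8%. None of the stated values is reproduced.

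**Could another reading produce them?**

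| Variant | SD 0.7 | SD 1.0 | SD 1.5 |
|---|---|---|---|
| Stated in the plan | 87.4% | 71.3% | 50.9% |
| 65/35, one-sided .05 | 95.9% | 76.5% | 47.4% |
| 50/50, two-sided | 94.3% | 69.7% | 37.9% |
| 75/40, two-sided | 95.1% | 71.6% | 39.3% |
| 100/50, two-sided | 98.4% | 81.8% | 48.1% |
| 55/30, two-sided | 87.5% | 58.6% | 30.6% |

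Taking the standardized difference as exactly 0.7 instead of 0.5/0.7 = 0.714 gives 91.1% in the base case, so rounding is not the cause. Some variants come close to one stated value (55/30 at SD 0.7, 75/40 at SD 1.0), but none fits all three. A search over arm sizes from 10 to 159, alphas of .01, .025, .05 and .10, and one- and two-sided tests found no combination within 2 points of all three.

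**Internal consistency.** λ is proportional to 1/SD, so the SD 0.7 value must be 1.0/0.7 = 1.43 times the SD 1.0 value and 1.5/0.7 = 2.14 times the SD 1.5 value, whatever the arm sizes. Back-solving with the normal approximation, λ = z(power) + 1.960:

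- 87.4%: 1.146 + 1.960 = 3.11
- 71.3%: 0.562 + 1.960 = 2.52
- 50.9%: 0.023 + 1.960 = 1.98

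The ratios are 3.11/2.52 = 1.23 and 3.11/1.98 = 1.57, not 1.43 and 2.14. With the one-sided constant 1.645 they are 1.26 and 1.67. Changing the sample size or allocation, or applying one common variance reduction (ANCOVA, change score or repeated measures with a single correlation), multiplies all three λ values equally and cannot repair this.

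Put another way, at a 65:35 split the stated two-sided powers need totals of about 85, 114 and 157. At 65 versus 35 they need two-sided alphas of about .027, .071 and .119.

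**The case against.** The strongest objection concerns sidedness. The power paragraph does not state it, the analytic plans make most tests two-sided but not all, and Hypothesis 1 is directional. If one-sided testing was meant, the worst case is 47.4%, the overstatement at SD 1.5 shrinks to 3.5 points, and the SD 1.0 figure becomes an understatement (71.3% against 76.5%). This is a fair condition on the 35.0%. It does not rescue the text, because one-sided testing reproduces none of the three figures.

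The base case is conservative: 87.4% is stated where the design gives 92.1%. The claim of adequate power at the design SD therefore survives, and the large error is confined to an SD that the plan expects its entry criteria to avoid. That stands and limits the seriousness.

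Recruitment has closed and the planned efficacy analysis is a mixed model, so correcting a t-test approximation changes no enrolment, endpoint or analysis. Confidence intervals, if reported, would show the precision achieved, and the observed SD will be available for the next trial. These points reduce the practical harm; they do not make the numbers right.

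Finally, any allowance for loss after randomization is an assumption, because the documents give no rate, and participants with at least one follow-up visit stay in the Full Analysis Set, with multiple imputation planned. Such an allowance is an addition and not part of the error.

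**Conclusion.** The concern holds. For 65 versus 35, a difference of 0.5, equal SDs and a two-sided t test at .05, power is 92.1%, 65.6% and 35.0%, against 87.4%, 71.3% and 50.9% in the plan. The stated figures are wrong for the stated design under either sidedness, and no single design gives all three. The 35.0% depends on two-sided testing, which is the better reading of the analytic plans, and on all 100 patients having a 12-month value. The errors run in both directions, and the one that matters is at SD 1.5: a probability of missing a true effect of 65.0% instead of the implied 49.1%. Because the design-case claim survives and nothing in the conduct of the trial changes, this is a correction that should be made, not a flaw that undermines the trial.

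**What to change.** State in the power paragraph that the test is two-sided at .05, and replace the three figures with 92.1% (SD 0.7), 65.6% (SD 1.0) and 35.0% (SD 1.5) for 65 versus 35. If the sponsor used another method or other inputs, state them and recompute all three cases on that one basis.

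Optionally, add a line showing the same powers after loss between randomization and month 12, labelled as an assumption. With the same formula, two-sided and counting only observed 12-month values, illustrative losses give:

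| Assumed loss | Arms | SD 0.7 | SD 1.0 | SD 1.5 |
|---|---|---|---|---|
| 10% | 58/32 | 89.4% | 61.3% | 32.2% |
| 15% | 55/30 | 87.5% | 58.6% | 30.6% |
| 20% | 52/28 | 85.3% | 55.8% | 29.0% |

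The cost is wording only. Two of the three published figures become less favourable and one becomes more favourable.
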